#### 1.6 Pharmacokinetics of Aggrenox in ESRD

There are no reported pharmacokinetic studies of Aggrenox in patients with ESRD or on hemodialysis. As reported above, the combination of extended release dipyridamole and low dose aspirin similar to Aggrenox has been given safely to over 450 hemodialysis patients (unpublished results, Boehringer Ingelheim). Baseline adverse events were high in the placebo group but addition of Aggrenox did not lead to an excess of adverse events compared to that expected in patients with normal renal function. Dipyridamole alone has been used in standard doses (225 mg per day) in patients with renal disease or on hemodialysis and the complications have been similar to those reported for patients with normal renal function (34, 115). Dipyridamole is highly protein bound and metabolized by the liver to the monoglucuronide that is almost exclusively excreted into bile with only minute amounts excreted in the urine (116). These studies suggest that the drug will not be readily dialyzed and that no dose adjustment is needed for patients on hemodialysis. Aspirin and its metabolites are highly protein bound. The liver also rapidly metabolizes aspirin to salicyluric acid and various glucuronide derivatives. In contrast to dipyridamole, the kidney primarily excretes these metabolites. However, protein binding of aspirin and salicyclate is decreased in uremic subjects, and the total body clearance of aspirin has been shown to be faster in uremic subjects than controls (110). The small dose of aspirin in Aggrenox (25 mg per tablet) therefore will not need to be adjusted for renal insufficiency.

#### **1.7** Rationale for Performing the Study

Although native fistulas are preferred, there will be many patients for whom an arteriovenous graft will be the only possible vascular access. However, the median primary unassisted patency of PTFE grafts is less than 12 months and the median cumulative patency rate is less than 2 years (55, 56). Maintenance of cumulative patency requires frequent access related procedures engendering considerable discomfort for the patient and accumulating substantial costs to the health care system. The predominant cause of this high rate of failure is myointimal hyperplasia leading to stenosis and ultimately access thrombosis. Currently there is no proven therapy to ameliorate or prevent vascular access failure. However, the results from a small, randomized study have suggested that dipyridamole may be effective at reducing thrombosis of new PTFE grafts and that this effect might occur by inhibition of smooth muscle cell proliferation leading to access stenosis and failure. A large multicenter randomized placebo-controlled trial with sufficient power to detect whether dipyridamole has a clinically significant effect to prevent vascular access failure is needed. The present study is designed to test whether dipyridamole in the form of Aggrenox can prolong primary unassisted patency of newly created AV grafts. The use of standardized flow monitoring and imaging of grafts with declining flow rates will further provide important mechanistic information on the efficacy of Aggrenox to prevent access stenosis.

# 2. OBJECTIVES AND DESIGN

#### 2.1 Objective

To determine whether Aggrenox (Boehringer-Ingelheim) prolongs primary unassisted patency in newly created arteriovenous grafts.

#### 2.2 Design

The study will be a randomized double-blind, placebo-controlled multi-center trial of Aggrenox compared to placebo for the prevention of access failure in patients who receive a new arteriovenous graft. Eligible subjects will be enrolled and baseline data collected prior to the placement of a new graft. Following successful placement of the graft, subjects will be randomized with equal allocation to therapy with either Aggrenox 1 capsule twice a day or a matched placebo. For randomization, subjects will be stratified by Clinical Center and whether the graft placement is in the lower arm or at another site (e.g., upper arm or leg) and whether or not the patient is using an ACE inhibitor or angiotensin receptor blocker at enrollment. The study medication will be started within 2 days of the access surgery and continued until the primary endpoint. The primary outcome will be primary unassisted patency, defined as the time from randomization until the composite endpoint of thrombosis or any access procedure required to maintain or restore access function (subsequently referred to as the first access event). Predefined secondary outcomes include 1) the time from randomization to site failure, 2) time from randomization to death, and 3) time from randomization to the composite outcome of site failure or death. The study participants will be followed monthly to measure access flow rate and record access related complications, adverse drug reactions, hospitalizations, and medication compliance until the primary endpoint is reached. Monthly measurement of access flow rate will be used to detect a hemodynamically significant stenosis before it leads to access thrombosis. A drop in monthly access flow rate that meets pre-specified limits will trigger angiographic evaluation and repair of the access if a 50% or greater stenosis is observed. The study drug and active monitoring will be discontinued when the primary endpoint is reached. Further follow-up will be limited to determining whether total access site failure or death occurred prior to

study closeout and if so, the time of that event. It is anticipated that the study will enroll a total of 1056 subjects to have an 85% power to detect a 25% treatment effect. This projected sample size will incorporate a statistical stopping rule, which will allow the External Advisory Committee to terminate the study early if therapy with Aggrenox is proven to be effective or if it becomes clear that the null hypothesis is unlikely to be disproved.

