# 3.3 Randomization

Subjects who have been enrolled in the study will be randomized within 2 days after successful placement of a new arteriovenous graft. Administration of the study drug should begin immediately following randomization. The optimal time for randomization and initiation of study medication would be in the postoperative recovery room after verification that a graft was placed. If the surgeon reports that the graft thrombosed in the operating room or in the recovery room, the patient should not be randomized. Subjects will be randomized to either Aggrenox or matched placebo in a ratio of 1:1. Randomization will be stratified by Clinical Center and by access (lower arm or at another site). A random permuted block design will be used to assure approximate balance over time. Randomization will be performed via the internet using a Web browser following verification of eligibility by the Data Coordinating Center. Stratification based on Clinical Center is designed to minimize the influence that differences in baseline risk between different centers might have on study outcome. While one source of variability is likely to be surgical expertise (62), the number of access procedures done by each surgeon is expected to be so small that stratification by surgeon is not likely to be feasible. The location of the graft in the upper or lower arm has been shown to strongly influence graft survival in some studies and thus randomization will also be stratified by this variable (55, 63, 64). Since leg grafts and other heroic graft sites (e.g., necklace graft) have a high flow rate, they will be categorized as an upper arm graft for the purpose of stratification (63).

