Use of angiotensin converting enzyme inhibitors has recently been reported in two retrospective studies to have a strong effect to prevent access failure (119, 120). The results are preliminary, however, the use of ACE inhibitors in dialysis patients is increasing. If ACE inhibitors or ARBs do have a large effect on access survival then this could impact on the response to Aggrenox. Therefore, whether a patient was on an ACE inhibitor or ARB at baseline will be included as a prespecified covariate in the primary analysis. The use of these agents will not be controlled and may change during the course of the study. The ongoing use of these agents will be recorded at the monthly visits and that data will be used to further analyze for a possible relationship between use of these agents and access failure. In addition, hypoalbuminemia has been reported to be a strong risk predictor of access failure (55, 63, 64). Therefore, serum albumin at baseline will be included as a second prespecified covariate in the primary analysis. Other potential prognostic factors such as diabetes and vascular disease have not been consistently shown to be strong predictors of access failure, and will not used as stratification factors or as covariates in the primary analysis.

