#### 9.2.2.2 Primary Analysis

The primary statistical analysis will compare the effects of the Aggrenox and placebo interventions on primary unassisted patency as in Section 7. This analysis will be conducted using a Cox proportional hazards regression analysis (85) with stratification by Clinical Center and graft location (lower arm vs. another site). ACE inhibitor or ARB usage at baseline and serum albumin at baseline will be included as pre-specified covariates. The comparison of the Aggrenox and placebo interventions in the primary analysis will be carried out using an intent-to-treat strategy in which patients are retained in their randomized groups regardless of their compliance to the treatments. A 2-sided hypothesis test will be conducted at the 5% level of significance.

In accordance with the intent-to-treat format, events defining the primary unassisted patency outcome which occur after medication stop points will be counted as events in the primary analysis. However, the primary Cox regression analysis will be censored at the following events: death, renal transplant, switch to peritoneal dialysis or home dialysis, or transfer to a center not participating in the trial. Censoring these events is consistent with previous studies of access survival (34, 56, 86-88), and is necessary because the alternative strategy of incorporating them in the primary outcome would unacceptably reduce the hypothesized treatment effect. However, because they occur frequently in dialysis patients, it is recognized that censoring these events exposes the primary treatment comparison to the possibility of bias due to informative censoring (89).

The cumulative incidence of events for the primary outcome will be summarized graphically by Kaplan-Meier survival curves in which death, transplant, modality switches, and transfers are censored. The Kaplan-Meier curves will estimate the distribution of unassisted patency assuming independent censoring in a hypothetical population where the censoring events are assumed not to occur. In addition to the standard Kaplan-Meier curves, we will summarize the marginal cumulative incidence of the composite outcome while treating death, transplant, and modality switches as competing risks (90, 91). In this approach, the cumulative incidence curves estimate the marginal cumulative probabilities of occurrence of the composite event while acknowledging the absence of the composite event following death, transplant or modality switches.

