#### 9.2.2.4 Secondary Outcomes

Time from randomization to the secondary outcome of site failure will be analyzed using a Cox regression model similar to that used in the primary analysis, with the same stratification factors, adjustment for baseline serum albumin and the same censoring variables. Time from randomization to death, and time from randomization to the composite of death or site failure will also be analyzed by Cox regressions with the same stratification factors and adjustment for baseline albumin as in the primary analysis. As for the primary analysis, censoring events include renal transplant, switch to peritoneal dialysis or home dialysis, or transfer to a center not participating in the trial. Cox models with cause-specific hazard rates will be used to analyze the specific cause of the primary events (e.g., events may be classified as being triggered by stenosis or clotting).

The effect of Aggrenox on the change in access blood flow over time (considered as a continuous variable) will be examined by longitudinal mixed effects models (100) or generalized estimating equations (101, 102). Joint models incorporating the longitudinal changes in access blood flow and the time-to-first access procedure will also be considered (103).

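### Sections 2.2 and 3.3 of the protocol disagree on whether ACE inhibitor/ARB use is a randomization stratum, and the secondary models leave that factor out without a reason

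*Protocol*

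**What the plan says.** **Allocation.** Protocol Section 2.2 (Design) says that, for randomization, "subjects will be stratified by Clinical Center and whether the graft placement is in the lower arm or at another site", and adds a third factor in the same sentence: "whether or not the patient is using an ACE inhibitor or angiotensin receptor blocker at enrollment". Section 3.3 (Randomization) gives two factors: "Randomization will be stratified by Clinical Center and by access (lower arm or at another site". The same section fixes the method: "A random permuted block design will be used to assure approximate balance over time".

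**Role of ACE inhibitor/ARB use.** Section 3.3 discusses these drugs separately and concludes that "whether a patient was on an ACE inhibitor or ARB at baseline will be included as a prespecified covariate in the primary analysis". Serum albumin is the second covariate.

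**Primary model.** Section 9.2.2.2 specifies a Cox regression "with stratification by Clinical Center and graft location (lower arm vs. another site"), and then: "ACE inhibitor or ARB usage at baseline and serum albumin at baseline will be included as pre-specified covariates".

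**Secondary models.** Section 9.2.2.4 calls the site-failure model similar to the primary one, "with the same stratification factors, adjustment for baseline serum albumin and the same censoring variables". For death, and for death or site failure, it again names the same strata and baseline albumin. ACE inhibitor/ARB use is not named for any of the three outcomes.

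**The concern.** The list of stratification factors determines how the allocation lists are built and what a site must enter before a patient can be allocated. Under Section 2.2 a center has to record ACE inhibitor/ARB status correctly before randomization; under Section 3.3 it does not. The two sections cannot both describe the permuted-block lists in use. Someone who audits the allocation, or writes the methods section of a report, could not tell from the protocol which is right.

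The same ambiguity carries into the analysis. The usual practice is to account in the model for every factor used in randomization. If ACE inhibitor/ARB use was a stratum and predicts outcome, a model that ignores it gives standard errors that are too large on average. The test is then conservative and some precision is lost. If it was not a stratum, the secondary models simply use a different covariate set from the primary model, with no reason given. A covariate choice left unexplained until after unblinding is open to the suspicion that it was made with the results in view.

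**Working it through.** No stated figure is in dispute, so the check sets the sections side by side and counts cells.

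**Step 1. Compare the sections.**

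| Protocol section | Center | Graft site | ACE inhibitor/ARB | Albumin |
|---|---|---|---|---|
| 2.2, randomization | stratum | stratum | stratum | not named |
| 3.3, randomization | stratum | stratum | not a stratum; covariate in primary analysis | covariate in primary analysis |
| 9.2.2.2, primary model | stratum | stratum | covariate | covariate |
| 9.2.2.4, three secondary models | stratum | stratum | not named | covariate |

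Sections 3.3 and 9.2.2.2 agree with each other, and Section 2.2 stands alone. Section 3.3 gives a reason for each of its two strata. It also treats stratification factors and covariates as separate roles, so Section 2.2 cannot be read as loose wording for the same scheme. The only addendum in the statistical section (Section 9.1) concerns recruitment and follow-up time and does not touch randomization.

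**Step 2. Count the allocation cells.** Section 9.1 gives 7 Clinical Centers and 1056 subjects.

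- Section 3.3: 7 × 2 = 14 cells; 1056 / 14 = 75.4 subjects per cell on average.
- Section 2.2: 7 × 2 × 2 = 28 cells; 1056 / 28 = 37.7 subjects per cell on average.

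The counts show that the lists differ. They do not show harm, since permuted blocks can work with either cell size.

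**Step 3. Does Section 9.2.2.4 bring the factor back in?** Referring to the same stratification factors does not do so, because ACE inhibitor/ARB use is a covariate in the primary model and not a stratum. Calling the site-failure model similar to the primary one does not clearly do so either, because the sentence then lists what is carried over and names only one of the two covariates.

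**Step 4. Do the design figures depend on the answer?** The stated inputs are a one-year control failure probability of 0.54, a 25% reduction, 22% annual loss, 15% dropout, 1% drop-in and a two-sided 5% test. None involves the stratification factors. For example, the control median is 12 × ln 2 / (−ln 0.46) = 10.71 months and the treated median is 10.71 / 0.75 = 14.28 months, against 10.70 and 14.28 in Section 9.1. Accrual is 1136 × 0.31 × 3 = 1056. These hold under either scheme.

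**Step 5. How much imbalance could arise without the third stratum?** With 528 per arm, and taking the worst case of 50% prevalence as an assumption, the chance difference between arms in ACE inhibitor/ARB use has a standard deviation of √(4 × 0.25 / 1056) = 0.031, about 3 percentage points.

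**The case against.** The strongest reply is that the protocol points to one reading. Section 2.2 is a design summary. Section 3.3 is the operative section, it justifies each factor it uses, and the primary model in Section 9.2.2.2 follows it. One clause in a summary is probably a remnant, and the primary analysis adjusts for the factor in any case. This stands, and it limits the size of the point. It does not remove the contradiction, because the protocol nowhere says which scheme was programmed.

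On the secondary models, the reply is that Section 3.3 assigns the covariate to the primary analysis and Section 9.2.2.4 states its own set. Nothing requires the two to match, and an analysis plan that is not shown may say more. This also largely stands: if Section 3.3 is right, there is an unexplained difference and not an error. What remains is that the protocol names one of two prespecified covariates and gives no reason for dropping the other.

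A reader might infer more than the protocol supports:

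- **That the primary result is at risk.** It is not materially so, because the covariate is in the primary model under both schemes.
- **That a promised balance has been lost.** Section 2.2 makes no claim about the degree of balance, and the chance difference is about 3 percentage points (one standard deviation) at most.
- **That ACE inhibitor/ARB use affects death.** The protocol says nothing of the kind. Section 3.3 speaks only of access failure, cites two retrospective studies, calls the results preliminary and argues conditionally.
- **That 14 against 28 cells measures a loss.** It only shows that the lists would differ.

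**Conclusion.** The point holds as a contradiction in the description of allocation, joined to an unexplained covariate omission in three secondary models. Its weight is minor to moderate.

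The allocation rule is wrong in Section 2.2 or in Section 3.3. The internal evidence favors Section 3.3, but only the randomization program can settle it. The primary analysis is little affected, and no sample-size or power figure changes.

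For site failure, death, and death or site failure, the consequence depends on the answer. If Section 2.2 describes the true scheme, the models leave out a randomization factor, and inference is conservative to the extent that the factor is prognostic. Conservative here means some loss of precision and no inflated false-positive rate. If Section 3.3 describes it, the secondary models merely differ from the primary one without a stated reason. The size of any precision loss cannot be computed, because the protocol gives neither the prevalence of ACE inhibitor/ARB use nor an effect estimate.

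**What to change.** 1. Check the randomization program at the Data Coordinating Center and state the scheme actually used in identical terms in Sections 2.2 and 3.3. The cost is one check and one corrected sentence.
2. In Section 9.2.2.4, add baseline ACE inhibitor/ARB use as a covariate for site failure, death, and death or site failure, so that these models carry the same strata and covariates as the primary model. This settles the analysis under either scheme. Current medications are already part of the baseline data (Section 6.1), so nothing new has to be collected, and the downside is one extra term in each model. If the omission was deliberate, the minimum is to state the reason.
3. Make both changes before any unblinded analysis of these outcomes and date them, so that the covariate set cannot appear to depend on the results.

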# 3. ENROLLMENT, RANDOMIZATION, AND BLINDING

The study population will be drawn from patients with end-stage renal disease or chronic renal failure approaching the need for dialysis who receive a new arteriovenous access at one of the participating Clinical Centers. Since the practice patterns at each participating unit will vary, the senior investigator and study coordinator at each unit will need to develop a strategy appropriate for their own unit to identify and recruit all eligible subjects. The potential subject should be approached prior to access surgery to provide information about the study and determine eligibility for enrollment. Subjects will be given time to read the informed consent documents and ask questions about their participation in the study. If the patient meets eligibility criteria and agrees to participate s(he) will be asked to sign the informed consent document and baseline enrollment data will then be obtained. It is preferred that this visit occur prior to placement of the new graft; however, enrollment will be permitted up to two calendar days following access surgery. Patient enrollment and baseline data collection will be take place within 45 days prior to randomization. If the surgery gets rescheduled for a date more than 45 days after the initial enrollment then new baseline data will need to be obtained. If more than 90 days elapses between the time of signing the original informed consent and the access surgery, the subject will be re-apprised about the study and a new informed consent document as well as new baseline data will be obtained.

#### 3.1 Inclusion Criteria

The inclusion criteria focus the study on relevant subjects within the study population who are likely to benefit from use of the study medication. Enrollment for this study will be open to both incident as well as prevalent adult hemodialysis patients who receive a new arteriovenous graft (either synthetic or biograft) and are able to give informed consent. The major goal of the study is to prevent the development of access stenosis. Limiting enrollment to subjects who receive a new arteriovenous graft (as opposed to including patients with prevalent grafts) maximizes the likelihood of preventing stenosis and is relevant to clinical practice. Starting Aggrenox when a new access is created mimics the protocol that worked in the study of Sreedhara et al. (34). More importantly, it maximizes the opportunity for Aggrenox to work by any of its proposed mechanisms of action, including inhibition of smooth muscle proliferation leading to the development of access stenosis or by decreasing platelet aggregation and thrombosis. The inclusion of prevalent accesses would have introduced several major problems into the study. Prevalent accesses are likely to have developed pre-existing stenoses that may be less amenable to drug therapy. In particular, prevalent accesses that have undergone a prior access procedure are less likely to respond to therapy with dipyridamole (34, 57, 58). Limiting enrollment to only those prevalent accesses that have not undergone a recent access procedure and otherwise are functioning well would decrease study feasibility by prolonging the expected event times. Overall, a negative study using prevalent accesses will fail to address the clinically important question of whether earlier initiation of Aggrenox would prevent access stenosis and failure (59-61). At this time most arteriovenous grafts are created using synthetic material (usually polytetrafluoroethylene or PTFE) placed in an upper extremity (forearm or arm). However, there is currently no evidence that the biology of access failure is any different in arteriovenous grafts composed of any other material (e.g., biografts) or placed at a site other than the upper extremity. For instance, a recent study has shown that survival of denatured homologous vein grafts was no different than synthetic PTFE grafts (118). With regard to access location, while upper arm straight grafts tend to have a better survival than forearm grafts (of any configuration), grafts placed at other sites such as the leg appear to have a survival similar to upper arm grafts (63). There is no evidence that the response to the study drug, Aggrenox, would be affected by the type of graft material or the location of the graft. Since inclusion of all arteriovenous grafts regardless of the type of material used or the location should make the study more relevant to current practice no limitation is placed on the type or location of the graft enrolled into the study.

The inclusion criteria are:

- 1. Age equal or greater than that at which consent can be obtained without parental involvement (18-21 years depending on state regulations).
- 2. Life expectancy of at least six months.
- 3. Chronic renal failure with anticipated start of hemodialysis within six months of enrollment, or current dialysis-dependence.
- 4. A new or planned AV graft placed in any location for the purpose of hemodialysis. (Any type of graft material and any configuration of the access is acceptable).
- 5. The patient is expected to stay at a participating dialysis facility for at least 6 months.
- 6. The patient's physician(s) will allow the patient to participate.
- 7. Ability to give informed consent.

